### Secondary Objective #1 (prediction of motivation states):

\*Predictors: Biosensor readings (blood glucose, physical activity, sleep), surveys (fear of hypoglycemia)

\*Dependent variable: Motivation states for physical activity

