# Physical activity with T1D has been linked to glycemic destabilization and fear of hypoglycemia.

Lack of engagement in physical activity stems from the unique challenges of physical activity with T1D. Physical activity with T1D can dysregulate blood glucose, leading to hypo- and/or hyperglycemia during and up to 24hr later due to consumption of energy, increased insulin sensitivity, release of counterregulatory hormones, and various combinations thereof. The direction and magnitude of these glycemic fluctuations vary according to type of physical activity, personal insulin sensitivity, insulin-on-board, and hormone concentrations. There is also high interindividual variation in these responses due to factors not well understood. Predicting these fluctuations to adjust diet and insulin is challenging.

When these fluctuations bring blood glucose into clinically unsafe ranges, symptoms can require halting of physical activity. As well, a context where these symptoms are likely (e.g., downward-trending blood glucose or high insulin-on-board) can preclude the start of physical activity. Furthermore, repeated exposure to these symptoms leads to *fear of hypoglycemia*, the most reported barrier to physical activity among people with T1D. This fear can motivate people with T1D to avoid physical activity due to remembering past symptoms and anticipating future occurrence of symptoms.

This investigation does not address exercise for type 2 diabetes (T2D) which faces different barriers compared to T1D. There is less risk of hypoglycemia due to the nature of the medication treatment, and therefore less fear of hypoglycemia. Meanwhile there is greater associated stigma, since the disease has etiology rooted in modifiable lifestyle behaviors. In addition, obesity as a comorbidity is more common and more severe. Therefore there is greater relevance of obesity-related barriers such as joint pain, exercise equipment being too small, and weight stigma.

August 13, 2024 Version #7

[figure not shown]

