### **SECONDARY**

Hypothesis 2-1-1: Fear of hypoglycemia and blood glucose trends over the past 3 hours will predict momentary motivation states for physical activity (timepoints T1-T2).

Hypothesis 2-1-2: Fear of hypoglycemia and glycemic metrics over the past week will predict motivation states for physical activity over the past week (timepoints T0-T2).

Hypothesis 2-2-1: Motivation states for physical activity over the past week will predict physical activity behavior change and adherence over the 4-week intervention period (T0-T1).

Hypothesis 2-2-2: Motivation states for physical activity over the past 3 hours will predict physical activity maintenance, over the 2 weeks following the intervention (T1-T2).

Protocol Number 2000035846

August 13, 2024 Version #7

Hypothesis 2-3: We expect interview themes among the proposed T1D population will include perception of connection among glycemic variation, fear of hypoglycemia, motivation states for physical activity, and performance of physical activity.

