# STUDY PROTOCOL

# **Social Behavioral Template**

#### 6.1.1 Data Collection

#### STUDY DESIGN OVERVIEW

The study is a single-group longitudinal study with periods of familiarization with devices, intervention using devices and mobile app, and maintenance follow-up (Figure 4). The primary aim is observing the intervention for feasibility, acceptability, and mathematical robustness. The secondary aim is observing psychological and biometric outcomes through assessments (Table 2) which are completed 1x/weekly during the entire study to test long-term effects (hypothesis 2-1-2 & 2-2-1) and 5x/daily during maintenance follow-up to test momentary effects (hypothesis 2-1-1 & 2-2-2). The secondary aim also includes an interview at the end of the study (hypothesis 2-3).

**Figure 4.** Individual participant timeline. Blue indicates measures for primary aims and red indicates measures for secondary aims.

Table 2. Surveys used for secondary aims. Appendix has instruments for dependent variable (#2a,2b), independent

variables fear of hypoglycemia (#3a, 3b), exercise self	-efficacy (#4), exercise self-regulation (#	
valence (#6), daily intention and competing demands  PHASE	Momentary	Weekly
	(Hypotheses 2-1-1, 2-2-2) (Timepoints T1-T2)	(Hypotheses 2-1-2, 2-2-1) (Timepoints T0-T2)
ASSESSMENT SCHEDULE	5x daily at random times within 3hr bins under ambulatory conditions of daily living	Weekly in controlled setting (tele-video in quiet room)
DEPENDENT VARIABLE††		
Cravings for Rest and Volitional Energy Expenditure (CRAVE) survey of motivation states for physical activity*	Score of 1-item want "right now" and 1-item aversion "right now"	Score of 5-item want "past week" and 5-item aversion "past week"
INDEPENDENT VARIABLES		
Fear of hypoglycemia†	Score of 1-item "next 3 hours" version	Weekly score of 18-item "past week" version
Fear of hyperglycemia ††	Score of 1-item "next 3 hours" version	Weekly score of 24-item "past week" version
Blood glucose metrics‡	Past 3 hours averages and slope	Weekly averages
Exercise self-efficacy 	N/A	Weekly score of 9-item "past week" version
Exercise self-regulation 	N/A	Weekly score 15-item "past week" version
COVARIATES		
Non-T1D-related affective valence states previously associated with CRAVE score (pleasure/displeasure  , activation/arousal  ).§	Score of 1-item "right now" versions	Weekly score of 1-item "past week" versions
Day of week, time of day	Timestamp	N/A

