Weather (temperature, humidity, windchill for GPS location by National Weather Service)	Momentary value	Weekly averages

August 13, 2024

Version #7

Physical Activity Daily Intention  multiple choices (exercise in morning, occupational activity, etc  )	Daily state	Weekly frequencies
Competing Demands "How busy is today's schedule?"82	Daily state	Weekly averages
Illness "Were you sick yesterday?"	Daily state	Weekly frequency
Sleep (total, waketime after sleep onset)**	Daily state	Weekly averages

††Dependent variable for aim 2-1. For aim 2-2, this is an independent variable and the dependent variable is Actigraph-measured physical activity. \*Validated in ref for 5-item versions and ref for 1-item versions. †1-item is emerging new instrument and 18-item widely validated ( $\alpha$ =.89). ††1-item parallels fear of hypoglycemia item one row up, and 24-item is validated ( $\alpha$ =.92). ‡Assessed by Dexcom G6 continuous glucose monitor (mean error 9%-10%). Quantified as consensus metrics (Coefficient of variation, mean, time in target range [70-180 mg/dL], time above range, time below range i.e. hypoglycemic). §.41-.88 convergent validity. ||assess at wakeup and apply to all timepoints that day. \*\*Assessed by Actigraph GT9X. Each 60-s epoch will be scored as wake or sleep (Sadeh's algorithm).

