# 7 Statistical Design

#### 7.1 Sample Size Considerations

This is a pilot study with primary objectives to test feasibility and acceptability, for which a typical sample size is 10-40 participants¹. Within this range we chose 24 participants to first ensure thematic saturation of interviews (aims 1-2, 2-3), and second achieve adequate power for one of the secondary objectives, specifically hypothesis 2-1-1. Based on my past retention and adherence among sedentary adults with and without T1D (88% participants completed, they provided 83% of ecological momentary assessments on longer surveys than the present study, 90% continuous glucose monitor wear, and 95% accelerometer wear) I expect 21 completers with an average of 50 complete observations each over T1-T2. Thus, using previous psychometrics of the CRAVE wants and aversions (.28/.39 ICC, 9.9/12.3 total variances) I expect design effects of 14.21/20.11 and standard errors of 0.37/0.48, yielding 91%/81% power to detect predictors having ≥ .34 correlation (e.g., pleasure, fear of hypoglycemia). For other secondary objective hypotheses (2-1-2, 2-2-1, 2-2-2) the study is not designed to detect statistical significance but calculate effect sizes (Cohen's f²) for purposes of determining whether the WANT, SCT model, or both generate a signal for prediction of physical activity behavior.

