#### 7.2.1 Secondary Objective Analyses (if applicable)

All statistical models for secondary objectives 1 and 2 will estimate intraclass correlation coefficient (ICC) to assess the proportion of variance explained by participant ID.

Secondary Objective 1 (STATISTICAL, MULTILEVEL MODELING). Examine whether recognized T1D-related physical activity barriers (fear of hypoglycemia, glycemic variation) predict momentary and long-term variation in motivation states for physical activity

**Hypothesis 2-1-1. Momentary predictors of motivation states.** We will develop two multilevel models for the dependent variables of want and aversion for physical activity (CRAVE 2-item "right now") respectively. The independent variables and covariates (Table 2) will be separated into momentary states for level 1, daily states for level 2, and demographics for level 3.

Hypothesis 2-1-2. Week-to-week changes in motivation states. We will develop two generalized linear mixed models for the dependent variables of want and aversion for physical activity (CRAVE 10-item "right now") respectively. A random intercept will incorporate correlations within-subject. We will include long-term assessed independent variables and covariates (Table 2, last column) along with a time categorical variable to estimate the contribution of changes coinciding with intervention (T0 to T1) and maintenance follow-up (T1 to T2).

Secondary Objective 2 (STATISTICAL, MULTILEVEL MODELING). Examine whether motivation states for physical activity predict momentary and long-term variation in physical activity behavior change, adherence, and maintenance resulting from a T1D motivational physical activity intervention.

August 13, 2024

Version #7

Hypothesis 2-2-1 – Predictors of physical activity behavior change and adherence over the intervention. We will develop a generalized linear mixed model for physical activity behavior testing WANT and SCT constructs as independent variables. A random intercept will incorporate correlation within-subject. We will include long-term assessed independent variables and covariates (Table 2, last column) along with a time categorical variable to estimate the contribution of changes from intervention (T0-T1) and maintenance follow-up (T1-T2).

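### Table 2 and Section 7.2.1 give Hypotheses 2-1-1 and 2-1-2 no measured-activity term, although the synopsis lists activity as a predictor, so glucose coefficients may partly reflect recent activity

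*Combined protocol and SAP*

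**What the plan says.** Hypothesis 2-1-1 (Section 3.2) reads: "Fear of hypoglycemia and blood glucose trends over the past 3 hours will predict momentary motivation states for physical activity". Section 7.1 chose the sample size partly to "achieve adequate power for one of the secondary objectives, specifically hypothesis 2-1-1"; for the other secondary hypotheses it plans effect sizes only. Two models are fitted, one for want and one for aversion.

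For their content, Section 7.2.1 states: "The independent variables and covariates (Table 2) will be separated into momentary states for level 1, daily states for level 2", with demographics at level 3. In Table 2 (Section 6.1.1) the momentary glucose predictor is "Past 3 hours averages and slope". The other momentary or daily entries are fear of hypo- and hyperglycemia, affect and arousal, day and time, weather, intention, competing demands, illness and sleep. The nearest item to activity is "Physical Activity Daily Intention", a self-report taken at wake-up. Measured activity appears only in a footnote, for aim 2-2, where "the dependent variable is Actigraph-measured physical activity". The weekly column, which feeds Hypothesis 2-1-2, has no measured activity either.

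The synopsis entry for Secondary Objective 1 differs: "Predictors: Biosensor readings (blood glucose, physical activity, sleep), surveys (fear of hypoglycemia"). It gives no device, time window or model level for the activity predictor.

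**The concern.** Section 1.1 states that "Physical activity with T1D can dysregulate blood glucose, leading to hypo- and/or hyperglycemia during and up to 24hr later". Activity in the hours before a rating therefore acts on the key predictor. If having just been active also changes how much a person wants to be active now, recent activity is a common cause of predictor and outcome, and an unadjusted glucose coefficient absorbs part of its effect.

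The background section says the mechanism found is meant to guide tailoring, with one kind of message if glucose is the predictor and another if fear of hypoglycemia is. A glucose coefficient that mainly marks recent exercise could be read as a barrier mechanism. Because the synopsis and the detailed plan disagree, an analyst could also defend either model after seeing the results.

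**Working it through.** **Step 1. The plan's own figures.** Inputs from Section 7.1: 24 participants, 88% completion, 83% of momentary surveys, 90% CGM wear, 95% accelerometer wear, ICC .28/.39 (want/aversion), r = .34. Five surveys on 14 days give 70.

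- Completers: 24 × .88 = 21.1. Observations each: 70 × .83 × .90 × .95 = 49.7. Total: 21 × 50 = 1,050.
- Design effect, 1 + 49 × ICC: 14.72 for want (stated 14.21) and 20.11 for aversion (as stated).
- Effective N: 1,050/14.21 = 73.9; 1,050/20.11 = 52.2.
- Power, Φ(atanh(.34) × √(Neff − 3) − z): one-sided .05 gives 90.9% and 79.9%, close to the stated 91% and 81%. Two-sided gives 84.6% and 70.0%. The plan states neither alpha nor sidedness for 2-1-1; .05 is assumed because Hypothesis 1-3-3 uses it.

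**Step 2. The bias formula.** With no direct glucose effect, spurious r = r(activity, glucose) × r(activity, motivation). The documents give neither correlation, so ranges are shown. The simulation is a random-intercept model, 21 × 50, ICC .28, two-sided .05, 2,000 runs.

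| Both links | Spurious r | False positives, activity omitted | Activity included |
|---|---|---|---|
| .1 | .01 | 6% | 6% |
| .2 | .04 | 25% | 5% |
| .3 | .09 | 81% | 5% |
| .5 | .25 | 100% | 6% |

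At the plan's much smaller effective N (74/52), links of .3 give only 12%/10%. A spurious r of .34 needs both links near √.34 = .58.

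**Step 3. The same bias as exercise shifts.** Let activity occur in a share q of 3-hour windows. The pilot's 2.4 sessions a week over 35 windows gives .07. Five active days a week would give 5/35 = .14, rounded up to .15. A shift of d within-person SDs gives r = d√(q(1−q)) / √(1 + d²q(1−q)).

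Example: q = .07, slope −1 SD, want −0.5 SD of total, which is .5/√.72 = .589 within-person SD. Then √(.07 × .93) = .255; slope link .255/√1.065 = .247; want link .150/√1.023 = .149; product .037. With √(1,050 − 21 − 3) = 32.0, the false-positive rate is about Φ(.037 × 32.0 − 1.96) ≈ 22%. Simulation gives 21% to 24%.

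| q | Slope shift | Want shift | Spurious r | False positives |
|---|---|---|---|---|
| .07 | 0.5 | 0.5 | .02 | 9% |
| .15 | 0.5 | 0.5 | .04 | 21% |
| .07 | 1 | 0.5 | .04 | 21%–24% |
| .15 | 1 | 0.5 | .07 | 61%–62% |
| .07 | 1 | 1 | .07 | 62%–65% |
| .15 | 1 | 1 | .13 | 99% |

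With activity in the model, these rates return to 4%–7%.

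**Step 4. Mixed glucose responses.** Every row above shifts slope the same way in everyone. Now let the shift average −0.3 SD, with assumed SDs of .7 between people and .6 between sessions, and the want shift in within-person SDs. A 0.5 SD want shift gives about 6%–7% (q = .07) and 10%–11% (q = .15). A 1 SD want shift gives about 10%–11% and 23%–24%. A mean shift of zero gives 5%–9%. Halving q to .035 with a uniform −1/0.5 shift gives 8%–9%.

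**Step 5. Cost of adjusting.** Power becomes Φ(atanh(.34) × √(Neff − 4) × √(1 − ρ²) − z), where ρ is the assumed correlation of activity with slope. At ρ = .3, one-sided, want goes from 90.9% to 88.1% and aversion from 79.9% to 75.8%.

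**The case against.** The strongest reply has five parts.

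- **Undocumented link.** The effect of past activity on current motivation is not in the documents. Section 1.2.3 reports only that want is associated with current or intended activity, which does not establish that direction. This stands, and it caps confidence at medium.
- **Direction of the glucose response.** Section 1.1 describes falls and rises and high variation between people, and the video library mixes aerobic and resistance work. Opposite responses largely cancel in a pooled slope. This stands; Step 4 shows how far it lowers the rates.
- **Activity rate.** The pilot rate comes from app use, whereas the momentary surveys run on days 50–64, after the app row in Table 1 ends. Table 1's time estimate does carry the 150-minute weekly target into follow-up, so the rate is uncertain in both directions.
- **Planned covariates.** Affect, arousal, time of day and intention may absorb part of any after-exercise effect. The simulations leave them out, so they may overstate the bias.
- **Mediation.** Glucose symptoms can halt or preclude activity (Section 1.1), so activity in the same window may lie on the path from glucose to motivation. This argues against relying on the adjusted estimate alone. It does not argue for leaving activity out.

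None of this reconciles the synopsis with Table 2.

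**Conclusion.** The inconsistency is certain: the synopsis names a measured-activity predictor, and the operative specification has none in the 2-1-1 or 2-1-2 models. The bias is conditional. It requires that recent activity affects current want or aversion and that its average effect on glucose slope differs from zero. Under weak links or mixed responses the false-positive rate stays near 5%. Moderate assumptions give about 10% to 25%. Rates above 60% in the shift settings need a uniform 1 SD fall in slope, combined with frequent activity or a large want shift.

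A reader might infer that the authors ignored activity altogether, or that a glucose finding would necessarily be spurious. The documents support neither: activity is in the synopsis, and the link to motivation is an assumption. Nor is this the plan's only power claim, since Hypothesis 1-3-3 also quotes one. No primary objective depends on this model, and the study is a 24-person pilot. Should-fix; confidence medium.

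**What to change.** Align Table 2 and Section 7.2.1 with the synopsis before analysis.

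- **2-1-1:** add a level-1 Actigraph term, either counts or moderate-to-vigorous minutes, in a window ending before the rating. State its time order relative to the glucose window. A shared window captures the most relevant activity but may include mediation; a window ending where the glucose window starts avoids that but misses activity within it.
- **2-1-2:** add past-week activity from Fitbit, which is worn in all weeks; Actigraph covers only days 8–22 and 50–64.
- **Reporting:** prespecify that glucose coefficients are shown with and without the activity term, and that glucose is interpreted as a barrier mechanism only if its coefficient persists after adjustment.

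The cost is wording plus the small power loss in Step 5. No new data are needed, and the planned 50 observations per person already allow for accelerometer wear. The downside is that adjustment may remove a genuine glucose effect that runs through activity, which is why both versions are reported.

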### Conceptual model of barriers to change.

Addressing this weakness, we and others have begun demonstrating that such affective (i.e., automatic) feeling states are the primary motivational factors driving humans to engage in physical activity. Furthermore, these motivational factors have highly transient effects, exhibiting more state than trait qualities. Our team developed the Wants and Aversions for Neuromuscular Tasks (WANT) model to explain these relationships based on Kavanaugh's model of affective motivation states determined by motive states, affective valence (pleasure/displeasure), and arousal/activation. Past models by contrast have relied exclusively on social cognitive theory (SCT) constructs (i.e., self-efficacy, outcome expectations, sociocultural traits). Therefore, we must test not only SCT constructs but also WANT model real-time states to link T1D-related barriers to physical activity (Figure 2).

In sum, our secondary objectives will address underlying psychological mechanisms of the intervention. Knowledge of these mechanisms would improve tailoring. For example, if we find an individual's lack of motivation for physical activity is predicted by having below-average starting blood glucose, a below-average blood glucose reading an hour before opportunities for physical activity would trigger a reminder for additional carbohydrates. On the other hand, if we find the predictor is *fear* of hypoglycemia, the message would provide psychological support such as cognitive behavioral therapy for fear of hypoglycemia. To generate the needed mechanistic knowledge, we have proposed the secondary aims of this study.

**Figure 2.** Hypothesized conceptual model of factors influencing physical activity behavior change. Dotted lines indicate alternative hypothesis that T1D-related barriers directly impact physical activity without mediation by motivation states.

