### 3.3 Objectives

Primary Objective 1. Evaluate the intervention for feasibility

Primary Objective 2. Evaluate the intervention for acceptability (i.e., user satisfaction)

**Primary Objective 3.** Evaluate the mathematical robustness of the intervention data-driven tools.

**Secondary Objective 1.** Examine whether recognized T1D-related physical activity barriers (fear of hypoglycemia, glycemic variation) predict momentary and long-term variation in motivation states for physical activity.

**Secondary Objective 2.** Examine whether motivation states for physical activity predict momentary and long-term variation in physical activity behavior change, adherence, and maintenance resulting from a T1D motivational physical activity intervention.

**Secondary Objective 3.** Qualitatively identify determinants and sequalae of motivation states for physical activity among adults with T1D.

August 13, 2024 Version #7

[figure not shown]

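### The two weekly models (Hypotheses 2-1-2 and 2-2-1) do not say how within-person and between-person association will be separated, so their slopes and f² cannot by themselves support a week-to-week or behaviour-change reading

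*Combined protocol and SAP*

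**What the plan says.** Section 7.2.1 plans a generalized linear mixed model for each weekly hypothesis. For 2-1-2 the outcomes are CRAVE want and aversion, and "A random intercept will incorporate correlations within-subject". For 2-2-1 the outcome is physical activity, and "A random intercept will incorporate correlation within-subject". Both take their predictors from the weekly column of Table 2: "We will include long-term assessed independent variables and covariates (Table 2, last column) along with a time categorical variable".

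Hypothesis 2-1-2 is headed "Week-to-week changes in motivation states", and 2-2-1 concerns behaviour change and adherence over the intervention. Section 3.3 frames Secondary Objective 1 as whether T1D-related barriers "predict momentary and long-term variation in motivation states for physical activity".

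For the momentary model (2-1-1, with the same levels reused in 2-2-2), predictors "will be separated into momentary states for level 1, daily states for level 2, and demographics for level 3". That sorts variables by how often they are measured. It does not divide one time-varying predictor into a stable part and a fluctuating part.

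The documents nowhere mention person-mean centring, person-mean covariates or participant fixed effects. Section 7.1 says that 2-1-2, 2-2-1 and 2-2-2 are not designed for significance testing. They are to yield Cohen's f², to show whether the WANT model, the SCT model or both give a predictive signal.

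**The concern.** A random intercept allows for correlated outcomes within a person. It does not remove differences between people from the slope of a time-varying predictor; it only down-weights them. The categorical time term removes only week effects that everyone shares, and the ICC planned for every model partitions outcome variance, not predictor effects.

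Two different statements therefore feed one coefficient: people who are generally more fearful are less motivated, and a given person is less motivated in weeks of greater fear. Only the second is a week-to-week association. The state-versus-trait distinction is central to the rationale in Sections 1.1 and 2.1, so a coefficient that blends the two leaves the question unanswered.

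The WANT-versus-SCT comparison is also exposed. The between-person share of a slope grows with the stability of the predictor, so a more stable construct could show a larger f² for that reason alone. The documents do not say which constructs are more stable.

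**Working it through.** **Plan's own figure.** There is none for the weekly models. The only power calculation (Section 7.1) is for momentary Hypothesis 2-1-1. Its design effect is 1 + (50 − 1) × ICC: for aversion 1 + 49 × .39 = 20.11, as printed; for want 1 + 49 × .28 = 14.72, against 14.21 printed. The standard errors are √(9.9 × 14.72 / 1,050) = 0.373 and √(12.3 × 20.11 / 1,050) = 0.485, against 0.37 and 0.48. The printed 91%/81% power is matched only with a one-sided .05 test, which Section 7.1 does not state. This point does not depend on that figure.

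**Inputs from the documents.**
- 21 completers; 50 momentary observations each; CRAVE ICC .28/.39 (Section 7.1).
- 9 weekly surveys, Visits 2 to 10 (Section 6.1.1).
- Actigraph on days 8-22 and 50-64 (Section 6.1.1, Mailing): 2 + 2 = about 4 outcome weeks for 2-2-1.

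**Assumed inputs.**
- Outcome ICC .34, between the two CRAVE values, borrowed for Actigraph activity, for which no ICC is given.
- Predictor ICC .28-.70.
- Correlation r of .34-.60 between people's stable levels of predictor and outcome. The low end equals the only reference correlation in Section 7.1.
- True within-person slope 0. Predictor and outcome have unit total variance.

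**Formulas.** With m observations per person, the balanced random-intercept slope is w × (between slope) + (1 − w) × (within slope), where
- k = (1 − ICCy) / (1 − ICCy + m·ICCy)
- B = ICCx + (1 − ICCx)/m
- W = ((m − 1)/m)(1 − ICCx)
- w = kB / (W + kB)

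With a within slope of 0, the between slope is r√(ICCx·ICCy)/B, and the spurious slope is w times that.

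**Worked case, m = 9, ICCx = .70, r = .60.** k = .66/(.66 + 3.06) = .177. B = .70 + .30/9 = .733. W = (8/9)(.30) = .267. w = .130/(.267 + .130) = .328. Between slope = .60 × √(.70 × .34)/.733 = .399. Spurious slope = .328 × .399 = 0.131.

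| m | ICCx, r | w | Between slope | Spurious slope |
|---|---|---|---|---|
| 9 | .28, .34 | .091 | .291 | 0.026 |
| 9 | .70, .60 | .328 | .399 | 0.131 |
| 4 | .28, .34 | .218 | .228 | 0.050 |
| 4 | .70, .60 | .530 | .378 | 0.200 |
| 50 | .28, .34 | .015 | .356 | 0.005 |
| 50 | .70, .60 | .082 | .415 | 0.034 |

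**Simulation.** Fitting the random-intercept model by REML to 21 simulated people under these assumptions gives about 0.03-0.13 (9 weeks) and 0.05-0.21 (4 weeks), in line with the table. A second set, with outcome ICC .28 or .39 and predictor ICC .39 or .70 (1,000 replicates per setting), gave 0.03-0.16 and 0.06-0.22. After splitting into person mean and deviation, its within-person slope averaged −0.011 to 0.017.

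**Rough f².** Taking R² as the squared slope, f² = slope²/(1 − slope²). At 9 weeks, 0.03 and 0.13 give 0.001 and 0.017. At 4 weeks, 0.05 and 0.21 give 0.003 and 0.046.

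**The case against.** The strongest reply is that these analyses are secondary, unpowered and effect-size-only, in a 24-person feasibility pilot. That stands. In simulation the unsplit weekly slope reached two-sided .05 significance in 7-34% (9 weeks) and 9-40% (4 weeks) of trials. A reader might infer a failed test, but the plan does not rely on a test there. The relevant damage is to the slope and f², and the implied f² values above are modest.

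A reader might also infer that any weekly finding will be nothing but stable differences between people. The documents do not support that. They are silent on centring rather than committed to raw scores, and a within-person slope of 0 is the worst case. In general the slope is a mixture.

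A third tempting inference is that a trait difference would pass straight into tailoring. The tailoring example in Section 1.1 ("if we find an individual's lack of motivation for physical activity is predicted by having below-average starting blood glucose") concerns glucose shortly before activity, which is momentary. With 50 observations the between-person weight is only about 2-8% over the assumed range. Section 6.1.1 assigns the weekly surveys to long-term effects.

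It can also be said that long-term variation may legitimately include differences between people. If so, they should be estimated separately; a blend answers neither question.

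Finally, splitting everything is not feasible. The weekly column of Table 2 holds about 19 time-varying variables: two fear scores, five glucose metrics, self-efficacy, self-regulation, two affect items, three weather items, intention, demands, illness and two sleep measures. Adding want and aversion for 2-2-1, and dropping one redundant time-in-range percentage, gives about 20. That many person means plus an intercept would nearly or fully exhaust the between-person information from 21 completers. This objection stands, and it limits the fix.

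**Conclusion.** The point holds for the two weekly models. As written, neither slope nor its f² can by itself support the week-to-week or behaviour-change reading, because the plan states no separation of within-person from between-person association. The between-person weight is about 9-33% with 9 surveys and 22-53% with about 4 Actigraph weeks. If nothing happens within people, the spurious standardised slope is about 0.03-0.13 and 0.05-0.21 respectively.

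The sizes rest on assumed predictor ICCs and stable correlations, a borrowed outcome ICC for 2-2-1, a single predictor and balanced data. The existence of the mixing does not depend on those values. The primary objectives are untouched, and the one powered secondary hypothesis (2-1-1) is little affected. This is a worthwhile, inexpensive clarification of secondary analyses, made before the data are analysed.

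**What to change.** In Section 7.2.1, for the two weekly models only, state that each hypothesised predictor enters as two terms: the person's mean over the analysed weeks and the weekly deviation from it.

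- For 2-1-2: fear of hypoglycemia and one key glycemic metric, named in advance.
- For 2-2-1: CRAVE want and aversion, exercise self-efficacy and exercise self-regulation.
- Report Cohen's f² for each part. Base week-to-week and behaviour-change conclusions, and the within-person part of the WANT-versus-SCT comparison, on the deviation terms. Treat the person-mean terms as descriptive.
- Do not add person-mean terms for the remaining Table 2 covariates.
- Applying the same split to the named predictors in 2-1-1 and 2-2-2 is optional.

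The cost is some plan wording, two derived columns and one extra coefficient per hypothesised predictor: two more in 2-1-2 and four more in 2-2-1. No new data are needed. The downside is that with about 21 completers the between-person estimates will be imprecise, which is why they should be descriptive.
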